#### Possibly related

- The AE follows a reasonable temporal sequence from IMP administration but could have been produced by the patient's clinical state, medical history, or the trial procedures/conditions.

Alternative etiology should be provided for all AEs assessed as possibly related to the IMP.

#### Probably Related

The AE is probably related to the IMP, which means the AE:

- Follows a reasonable temporal sequence from IMP administration
- Abates spontaneously upon discontinuation of the IMP (de-challenge) without any curative treatment
- Is confirmed by reappearance of the same reaction on repeat exposure (re-challenge) (if applicable)
- Cannot be reasonably explained by the known characteristics of the patient's clinical state or medical history

### **9.6.8 Action Taken with the Investigational Medicinal Product**

The action taken with the IMP should be noted as:

- Dose decreased
- Drug postponed
- Drug discontinued
- None
- Not Applicable\*
- Unknown

\* Should be used if the AE occurs before the first treatment, IMP has been discontinued for other reasons, or after the EOT

### **9.7 Events Requiring Immediate Reporting**

The following events (for reporting periods, see [Figure 9-1](#)) require reporting to the Sponsor within 24 h of knowledge (for details, see section [9.5](#)):

- SAE
- AESI
- DLT
- Pregnancy

#### **9.7.1 Pregnancy**

Any pregnancy, including partner pregnancy, that occurs during trial participation must be reported to the Sponsor within 24 h of knowledge using the pregnancy form. Pregnant trial patients must be discontinued from IMP treatment immediately (see section [6.3.3](#)). The pregnancy must be followed up to determine the outcome and status of the mother and the child. The child must be followed at least to the age of 1 month. Pregnancy complications and elective

terminations for medical reasons must be reported as an AE or SAE. Spontaneous abortions must be reported as an SAE.

## 9.8 Initial Reporting of Adverse Events

### SAEs/AESIs/DLTs

- The paper clinical AE report form must be reported from the site to the Sponsor within 24 h of the Investigator's first knowledge of the event. The paper clinical AE report form is to be sent to the designated drug safety provider.

### All AEs

- The eCRF AE form should be updated in accordance with agreed data entry timelines (see section 14.1.2).

The eCRF completion instructions for reporting of AEs should be followed.

## 9.9 Follow Up on Adverse Events

### SAEs/AESIs/DLTs

- New follow-up information available at the site must be reported within 24 h of knowledge.
- Follow-up information requested from the Sponsor must be replied to within 3 working days. The eCRF AE form should be updated in accordance to agreed data entry timelines (see section 14.1.2).
- If an ongoing SAE/AESI changes in intensity, relationship to IMP, or as new information becomes available for the event, the paper clinical AE report form should be completed and sent to the designated drug safety provider within 24 h of the change in assessment.
- Grade 3 or higher non-serious AEs that are considered treatment related and all SAEs, AESIs, and DLTs should be followed on a regular basis, according to the Investigator's

clinical judgment, until the event has been resolved or until the Investigator can assess it as chronic or stable. This includes follow-up after EOT.

### **Non-SAEs**

Non-serious AEs should be followed until they are either resolved, returned to baseline, or until the end of trial for the patient, whichever comes first.

#### **9.9.1 Reporting of SUSARs**

The Sponsor will ensure that all relevant information about suspected unexpected serious adverse reactions (SUSARs) is reported to the regulatory authorities in accordance with regulatory requirements.

The contract research organization (CRO) appointed by the Sponsor will notify the Investigators of SUSARs in accordance with local requirements. Furthermore, the Investigators will be informed of any trial-related SAEs that may warrant a change in any trial procedure. The CRO appointed by the Sponsor will inform the institutional review boards (IRBs)/independent ethics committees (IECs) of SUSARs in accordance with local requirement, unless locally this is an obligation of the Investigator.

The Sponsor's assessment of expectedness for nivatrotamab will be performed according to the current version of the IB.

#### **9.9.2 Communication of significant safety issues**

In the event of any significant safety-related issues, the Sponsor will decide upon immediate action to be taken, including prompt notification of the DMC, and will communicate to the regulatory authorities, Investigators, IECs/IRB, and patients, as needed, within regulatory timelines.

#### **9.9.3 Data Monitoring Committee**

An external DMC will be established to assure patient safety and will function independently of all other individuals associated with the conduct of the trial, including the site Investigators participating in the trial. The DMC will consist of a minimum of 2 physicians whose expertise covers relevant specialties.

During the conduct of phase 1 of the trial, after completion of the DLT evaluation period (2 treatment cycles/28 days) for the last patient in each dose level, the DMC will evaluate the available safety information and recommend trial continuation or termination. If continuation is recommended, the DMC will recommend to the Sponsor whether the dose should be escalated, de-escalated, or held at the same dose level.

During phase 1 and until the DMC meeting in phase 2, the Sponsor will share with the DMC all SAEs occurring during the trial, and an unplanned DMC meeting can be held at the request of either the DMC or the Sponsor safety committee.

During the conduct of phase 2, an additional DMC meeting will be held when the 10th patient across cohorts has completed Cycle 1 to evaluate whether the trial should be modified, stopped, or continue unchanged.

The Sponsor safety committee will evaluate the recommendations provided by the DMC after each DMC meeting. Any significant finding/recommendation from the DMC and endorsed by the Sponsor safety committee will be communicated to the regulatory authorities and IRB/IEC as appropriate, and to the sites.

Responsibilities, procedures, content of the DMC packages, and workflow of the DMC are specified in the DMC charter.

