### **6.2.5 Trial Stopping Rules**

If any of the following occur, administration of the IMP will be stopped, and recruitment will be put on hold at least temporarily until DMC feedback is received to confirm if the trial can continue:

- 1) One or more patients experience unexpected, sudden death during the treatment period
- 2) Treatment related death before the EOT visit
- 3) SAEs or frequency of AEs that, in the judgement of the Sponsor, are deemed to warrant immediate review by the DMC.
- 4) Any other safety finding assessed as related to nivatrotamab that, in the opinion of the DMC or Sponsor, contraindicates further dosing of trial patients.

If any of these occur, an immediate cumulative review of safety data with focus on the SAE/ AE in question will be conducted by the DMC to determine whether dosing and further recruitment should be resumed, the protocol modified, or whether the trial should be discontinued. Review and approval of the Sponsor Safety Committee is required for resumption of the trial in case the trial is interrupted due to one of the above-mentioned safety findings.

When applicable, regulatory authorities and ECs/IRBs will be notified of actions taken with the trial.

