## 15 PREMATURE TERMINATION OF THE TRIAL

### 15.1 Sponsor Criteria for Pausing Patient Enrolment

Enrolment will be paused if one of the following criteria is met:

- One or more patients experience unexpected, sudden death during the treatment period
- SAEs or frequency of AEs that, in the judgement of the Sponsor, are deemed to warrant immediate review by the DMC.
- One or more patients experience treatment-related death before EOT visit

If an above-mentioned criterion is met, the DMC will review the safety results and determine how to proceed as described in section [9.9.3](#).

Patients already included at the time of clinical trial pause, will continue in the clinical trial but further dosing will be postponed until a decision has been reached by the DMC.

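### Section 9.9.3 ends SAE sharing with the DMC, and unplanned DMC meetings, at the single planned phase 2 meeting, although the hold and pause rules rely on the DMC throughout

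*Combined protocol and SAP*

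**What the plan says.** Section 9.9.3 sets the DMC's information flow in one sentence. It opens "During phase 1 and until the DMC meeting in phase 2, the Sponsor will share with the DMC all SAEs occurring during the trial" and continues that "an unplanned DMC meeting can be held at the request of either the DMC or the Sponsor safety committee". Both commitments therefore carry the same time limit. The next paragraph of 9.9.3 plans one phase 2 meeting, set for when the 10th "patient across cohorts has completed Cycle 1 to evaluate whether the trial should be modified, stopped, or continue unchanged". No section commits to routine SAE sharing or a scheduled DMC review after that. Procedures and the content of DMC packages are left to a DMC charter, which is not among the documents.

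Other sections give the DMC a role with no phase limit:

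- Section 6.2.5 lists four triggers. Under any of them dosing stops and "recruitment will be put on hold at least temporarily until DMC feedback is received to confirm if the trial can continue", and the DMC reviews the cumulative safety data. Item 4 is "Any other safety finding assessed as related to nivatrotamab that, in the opinion of the DMC or Sponsor, contraindicates further dosing of trial patients".
- Section 15.1 says that after a pause "further dosing will be postponed until a decision has been reached by the DMC", and points to 9.9.3 for how the DMC proceeds.
- Section 15.2 gives a DMC recommendation as one example of a reason to discontinue the trial.
- Section 9.9.2 covers significant safety issues: "the Sponsor will decide upon immediate action to be taken, including prompt notification of the DMC".

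The phase 2 primary objective (section 5.1.1) is long-term safety at the RP2D. Treatment runs for up to 13 cycles of 14 days, and related SAEs are recorded up to 12 months after the last dose (section 6.2.13.2).

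**The concern.** Sections 6.2.5 and 15.1 assume a DMC that can act at any time, while 9.9.3 assures it of SAE data and of a way to convene only up to an early point in phase 2. The mismatch is sharpest for item 4 of 6.2.5, where the DMC's own opinion can start a hold. A committee that is not sent the SAEs has no assured basis for that opinion, and cannot notice a pattern of events that the sponsor has not itself judged significant. The cross-reference in 15.1 has a similar weakness, because for most of phase 2 it leads to a section whose unplanned-meeting provision has, as worded, run out.

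What is at stake is independent review of repeat dosing in the later phase 2 patients, which is the exposure that the long-term safety objective is about.

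**Working it through.** **The passages side by side, after the planned phase 2 meeting**

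| Route to the DMC | Who starts it | Assured after the meeting? |
|---|---|---|
| All SAEs shared (9.9.3) | Routine | No, stated end point |
| Unplanned meeting (9.9.3) | DMC or Sponsor safety committee | No, same sentence |
| Sudden unexpected or treatment-related death (6.2.5 items 1 and 2; 15.1) | The event | Yes |
| SAEs or AE frequency needing immediate review (6.2.5 item 3; 15.1) | Sponsor's judgement | Yes, at sponsor discretion |
| Finding against further dosing (6.2.5 item 4) | DMC or Sponsor opinion | Yes, but the DMC has no assured data for its part |
| Significant safety issue (9.9.2) | Sponsor's decision | Yes, at sponsor discretion |

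**How much of phase 2 falls after the meeting**

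Inputs from the protocol: 30 phase 2 patients (6.3.1); 13 cycles × 14 days = 182 days of treatment (synopsis); phase 2 recruitment of 6 months (6.2.6); meeting at the end of the 10th patient's 14-day Cycle 1 (9.9.3). The plan gives no exposure figure of its own to reproduce.

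Assumptions: even accrual over 182.6 days, so patient *i* enters on day (*i* − 0.5) × 182.6/30, that is, one patient every 6.09 days; the meeting is held on the day its trigger is met.

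1. Entry of patient 10: 9.5 × 6.087 = day 57.8. Meeting: 57.8 + 14 = day 71.8.
2. Patients dosed by then: patient 12 enters on day 11.5 × 6.087 = 70.0 and patient 13 on day 76.1. So 12 are dosed and 18 follow.
3. If all patients complete 13 cycles, the planned total is 30 × 182 = 5,460 patient-days. Accrued by the meeting: 12 × 71.82 − 6.087 × 72 = 424 patient-days (72 is the sum of 0.5, 1.5, …, 11.5). 424/5,460 = 7.8%, so about 92% comes later.
4. Many patients will stop earlier. With exponential treatment duration of median *m* months, expected treated days up to time *t* since entry are (1 − exp(−λ·min(*t*, 182)))/λ, with λ = ln 2/(30.44 *m*). Summed over the 30 entry dates:

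| Assumed median (months) | Patient-days by meeting | Total | Share before | Share after |
|---|---|---|---|---|
| 1.4 | 298 | 1,749 | 17.0% | 83% |
| 2 | 328 | 2,303 | 14.3% | 86% |
| 3.5 | 365 | 3,200 | 11.4% | 89% |
| 3.9 | 370 | 3,363 | 11.0% | 89% |
| 6 | 388 | 3,943 | 9.8% | 90% |

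The medians from 1.4 to 3.9 months span the PFS medians that section 4.1 cites for relapsed disease. They serve only as a guide to treatment duration.

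5. Delay in holding the meeting. Sharing ends at the meeting, not at its trigger, so a delay raises the share seen. With 14 days' delay and full completion: day 85.8, 14 patients dosed, 14 × 85.82 − 6.087 × 98 = 605 patient-days, 605/5,460 = 11.1% before and 89% after. With 28 days' delay: day 99.8, 16 patients dosed, 16 × 99.82 − 6.087 × 128 = 818, or 15.0% before and 85% after. At the shortest median (1.4 months) the shares after the meeting are 77% and 71%.

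6. Last exposure: patient 30 enters on day 29.5 × 6.087 = 179.6. Treatment could then run to day 179.6 + 182 = 362, and 12-month follow-up to day 727.

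**The case against.** The strongest reply is that the DMC is not cut off. The two death triggers in 6.2.5 need no sponsor discretion, apply in both phases, and bring a cumulative DMC review. Section 9.9.2 has no phase limit. Item 4 names the DMC or the sponsor, so no stopping rule depends on the DMC's opinion alone. The trial is open-label and single-arm, the sponsor receives SAEs, AESIs and DLTs within 24 hours (section 9.7), SUSARs go to the authorities (9.9.1), and the unseen charter may already provide for continued sharing.

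Much of this stands. A reader might infer that the DMC can do nothing after the meeting, or that every later review depends on the sponsor choosing to call it; the death triggers rule both out. What remains is narrower. Outside deaths, the routes run through the sponsor's judgement, and the protocol assures the DMC of no SAE data of its own. A charter should not have to override an end point that the protocol states.

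Two further inferences are tempting but not supported:

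- *That detection should be compared between 10 and 30 patients.* Table 11-1 is correct: at N=30, 1 − 0.95^30 = 79% for a 5% event. The same formula gives 40% at N=10. But the DMC has also seen the phase 1 SAEs. If 6 to 9 phase 1 patients had been treated at the RP2D (an assumption), the figure is 1 − 0.95^16 = 56% to 1 − 0.95^19 = 62%. The N=10 figure therefore overstates the gap.
- *That the meeting comes too early, because the phase 2 flow chart carries a 2-cycle DLT period.* Section 6.2.3 ties that window to dose escalation, and section 11.3.3 restricts the DLT set to escalation patients. On the accrual above, 7 of the first 10 patients already have at least 28 days since first dose at the meeting. Waiting 14 more days would put about 2 more patients on treatment (14/6.09 = 2.3) before the first phase 2 review.

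**Conclusion.** The concern holds in this form: 9.9.3 puts an explicit end on SAE sharing and unplanned meetings that does not fit 6.2.5, 15.1 or the phase 2 objective. After the planned meeting the DMC has no assured SAE data for its own opinion under item 4 of 6.2.5.

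With even accrual over 6 months and a meeting on the trigger day, about 18 of 30 patients start afterwards. About 92% of on-treatment exposure comes later if all patients complete 13 cycles, and 83 to 90% with assumed exponential durations of median 6 down to 1.4 months. A 28-day delay in the meeting lowers the range to about 71 to 85%. Accrual pattern, treatment duration and delay are assumptions, but most phase 2 exposure lies after the meeting throughout the range shown.

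The documents do not show that the sponsor will in fact stop sending SAEs, only that nothing in the protocol commits it to continue. This is a cheap improvement.

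**What to change.** Amend section 9.9.3 so that:

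- the sponsor continues to share all SAEs with the DMC through phase 2, at least until 30 days after the last dose of the last phase 2 patient, which matches the all-SAE reporting period in section 9.5.2;
- related SAEs collected in the 12-month follow-up are forwarded as well;
- either the DMC or the Sponsor safety committee can call an unplanned meeting over the same period.

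Align the DMC charter, and check that the reference in 15.1 to 9.9.3 then leads to a procedure that applies throughout phase 2. Leave the timing of the planned phase 2 meeting as it is.

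The cost is a few words in one section, the forwarding of reports that already exist, and some DMC reading time.

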## 10 LABORATORIES

Laboratory assessments are outlined in detail in section [8](#).

### 10.1 Clinical Laboratory Assessments

See section [8.1.9](#).

### 10.2 Pharmacokinetic Assessments

See section [8.3](#).

### 10.3 Immunogenicity

See section [8.1.13](#).

## 11 STATISTICAL METHODS AND DETERMINATION OF SAMPLE SIZE

### 11.1 General Overview

The data will be summarized in tables, as appropriate, showing the number of patients with non-missing data (n), mean, standard deviation, median, minimum, and maximum for continuous data and counts and percentages for categorical data. Data will also be listed as deemed appropriate. All statistical analyses will be performed and data appendices created by using SASTM version 9.4 or later.

Any statistical tests will be 2-sided with an  $\alpha$  (significance) level of 0.05.

Data from patients who were screened but never started treatment will be listed. Screening failures will not be included in any of the analyses and summary tables.

The results will be presented by groups and total. In the dose escalation phase of the trial, groups will be defined by dose-levels, and in the dose expansion phase, groups will be defined by sensitivity/resistance to previous platinum therapy.

Patients in the dose escalation phase, for whom major inclusion/exclusion criteria and dose regimen are the same as for the patients in the dose expansion phase, may be included in the analyses and presentations of the dose expansion results.

For the sake of the statistical analyses and summaries, the baseline value is defined as the value collected at the time closest to, but prior to, the start of the first nivatrotamab administration. Measurements made on the same day as the first nivatrotamab administration are assumed to have been performed pre-treatment, unless recorded, or by this trial protocol stipulated, otherwise.

The statistical analysis plan (SAP) will describe in further detail the analyses presented below. Furthermore, handling and presentation of data, including demographics, baseline data, and other trial assessments, will be described in more detail in the SAP.

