#### **6.2.1.6      Determination of MTD and RP2D**

The mBOIN-based MTD will be preliminarily estimated statistically as the dose level with the observed DLT-rate closest to the target toxicity level (i.e., 28%), as described in section 11.4.2.

After the mBOIN-based dose-escalation algorithm has been completed, the DMC and the Sponsor will determine the MTD and the RP2D, both of which may differ from the aforementioned preliminary statistical estimate. The RP2D cannot exceed the MTD.

The selection of the RP2D will be based on pharmacokinetic, pharmacodynamic, safety and efficacy data from Phase 1. The selection of RP2D will be informed by exposure-response analyses (cf. Section 11.4.9) and Frequency and severity of AEs will be balanced with any observed dose response for clinical activity. In the absence of compelling results as interpreted by the DMC and the Sponsor, the RP2D will be the highest dose administered that does not exceed the MTD. If there is evidence that a dose level lower than the MTD (which might not have been reached at this stage) has adequate clinical activity (whether determined by imaging data, pharmacodynamics endpoints, or predicted efficacious dose), the DMC and the Sponsor's safety committee may decide that the RP2D has been determined and that the dose escalation may be stopped.

Based on the available data, the DMC may recommend introduction of intermediate dose levels in between the pre-planned dose levels and may also suggest changing the dosing frequency.

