#### 6.3.2.1 Inclusion Criteria

1. Signed and dated informed consent has been provided prior to any trial-related procedures.
2. Patient willing and able to comply with the trial protocol
3. Age  $\geq 18$  years at the time of informed consent
4. Histologically or cytologically proven SCLC. Radiographical relapse/progression after minimum 1 line of platinum-containing chemotherapy with PR or CR as the best response (not required for phase I) and not more than 3 prior lines of therapy

5. Measurable disease according to RECIST v1.1
6. ECOG performance status 0–1
7. Expected survival >3 months
8. Platelet counts  $\geq 100,000$  cells/mm^3
9. Hemoglobin  $\geq 9$  g/dL
10. Absolute neutrophil count (ANC)  $\geq 1000$  cells/mm^3
11. Adequate liver function defined by AST, ALT, alkaline phosphatase (ALP)  $\leq 3 \times$  upper limit of normal (ULN), and serum bilirubin  $\leq 1.5 \times$  ULN with the following exceptions
  - a. In patients with documented liver metastases, AST, ALT, and ALP  $\leq 5 \times$  ULN and serum bilirubin  $\leq 1.5 \times$  ULN
12. Adequate renal function with serum creatinine  $\leq 1.5$  mg/dL or creatinine clearance  $\geq 50$  mL/min as calculated using the Cockcroft-Gault equation
13. Serum albumin  $> 3.0$  g/dL
14. Women of child-bearing potential must agree to appropriate contraception during treatment and for a period of 30 days after the last dose of the study drug. Fertile male patients must agree to the use of condoms during treatment and for a period of 30 days after the last dose of the IMP. For a sterilized male patient to be exempt from the requirement to use contraception after IMP treatment, he must have undergone surgical sterilization (vasectomy).

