### 11.3 Analysis Populations of Interest

#### 11.3.1 Full Analysis Set

The full analysis set (FAS) will include all patients enrolled in the trial who received at least 1 dose of nivatrotamab. Patients who do not fulfil relevant inclusion criteria (e.g., no baseline measurable disease) but still receive the study drug, may be excluded from the FAS.

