#### **11.4.7 Analyses of Anti-tumor Activity**

The efficacy analyses will be based on the FAS.

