#### **11.4.12 Interim Analysis**

No formal interim analyses are planned. Ad-hoc interim analyses may be performed in relation to health authority interactions.

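### Does leaving phase 1 pooling and FAS exclusions optional bias the phase 2 response rate enough to need a change?

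*Combined protocol and SAP*

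**What the plan says.** Two sentences make the phase 2 efficacy set optional.

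- **Pooling (section 11.1).** Dose-escalation patients who share the major eligibility criteria and the dose regimen of the expansion patients "may be included in the analyses and presentations of the dose expansion results".
- **FAS exclusion (section 11.3.1).** "Patients who do not fulfil relevant inclusion criteria (e.g., no baseline measurable disease) but still receive the study drug, may be excluded from the FAS". Section 11.4.7 then states: "The efficacy analyses will be based on the FAS".

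The surrounding text matters too.

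- Section 11.1 defers detail: "The statistical analysis plan (SAP) will describe in further detail the analyses presented below". No separate SAP text was available for this check.
- Section 6.2.1.6 says of the dose for phase 2 (RP2D): "The selection of the RP2D will be based on pharmacokinetic, pharmacodynamic, safety and efficacy data from Phase 1". Without compelling results, "the RP2D will be the highest dose administered that does not exceed the MTD".
- Section 11.4.12 plans no formal interim analysis, but "Ad-hoc interim analyses may be performed in relation to health authority interactions".
- Inclusion criterion 4 (section 6.3.2.1) asks for prior platinum-containing chemotherapy "with PR or CR as the best response (not required for phase I"), so the two phases differ on this point.
- Phase 2 ORR is a secondary endpoint (section 5.2.2), reported with an exact 95% confidence interval (section 11.4.7.2). No null rate, target or power is given for it.

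**The concern.** The trial is open-label and has no comparator, so the phase 2 ORR will be read directly as evidence of activity. Phase 1 efficacy data feed the dose decision, so the sponsor will know the phase 1 responses before phase 2 results exist. If pooling is decided after both are known, the more favorable of two estimates can be reported. If non-responders who failed an inclusion criterion can be dropped at discretion, the denominator can shrink. And if the RP2D was picked because of its phase 1 responses, pooling those patients reuses the data that chose the dose. All three push the ORR upward.

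There is also an undefined term. Section 11.1 does not say whether the phase 2-only requirement for a prior platinum response is a major criterion, which decides whether phase 1 patients without such a response can enter the phase 2 ORR.

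**Working it through.** **The plan's own figures.** The plan gives no ORR sample-size calculation to reproduce. The only calculation tied to 30 phase 2 patients is Table 11-1, from 1 − (1 − p)^N. For p = 10% and N = 30 this gives 1 − 0.9^30 = 95.8%, printed as 96%; all 24 cells agree to within 1 point.

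**Inputs.**
- Phase 2 patients: 30 (section 6.3.1).
- Pooled phase 1 patients, m: 6 or 9 at a level (section 6.2.1.5). As an extreme, 19, which is the 9 plus all 10 extra patients allowed by section 6.2.1.4.
- True ORR, p: assumed 10% to 20%, equal in both phases. Section 4.1 says that response rates rarely exceed 15% in a typical clinical population. It also reports 30% for a recently approved drug, which is used here as a higher assumption.

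**1. Reporting the larger estimate afterwards.** With x ~ Bin(30, p) and y ~ Bin(m, p), the bias is E[max(x/30, (x+y)/(30+m))] − p, by exact enumeration:

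| p | m = 6 | m = 9 | m = 19 |
|---|---|---|---|
| 10% | +0.91 | +1.05 | +1.36 |
| 15% | +1.07 | +1.25 | +1.62 |
| 20% | +1.19 | +1.41 | +1.82 |
| 30% | +1.37 | +1.61 | +2.08 |

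(percentage points)

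For p = 10% to 20% and m = 6 or 9, the exact 95% interval reported with the larger estimate covers the true rate in 97.4% to 98.8% of trials. If ties are resolved toward the pooled set, the range is 96.0% to 97.9%. The lower limit lies above the truth in 1.2% to 2.2%, against a nominal 2.5%. At p = 30%, coverage is still 95.9% or more. Exact intervals are conservative at these sizes, and that slack absorbs the choice.

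**2. Dropping non-responders from the FAS.** Removing k of 30 multiplies the ORR by 30/(30 − k). 5/30 = 16.7% becomes 5/29 = 17.2% or 5/28 = 17.9%.

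**3. Both together.** With m = 9 and two excluded patients who could not respond, the reported ORR exceeds that in all 30 treated patients by 2.3 points at p = 15% (14.0% to 16.3%) and by 3.7 points at p = 30% (28.0% to 31.7%).

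**4. Reuse of dose-selection data.** Suppose the RP2D were simply the level with the best observed ORR among K equally active levels, always pooled. The bias is (30p + E[max of K draws from Bin(m, p)])/(30 + m) − p. For p = 10% to 20% and m = 6 or 9, this is +1.0 to +1.7 points for K = 2 and +1.7 to +2.6 for K = 3. Coverage is 94.8% to 97.3%. With K = 1, as under the default in section 6.2.1.6, it is 0. The worst cell (p = 15%, three levels of 9) has the lower limit above the truth in 5.0% of trials. It needs 27 patients on three levels, against 18 to 23 expected in all of phase 1 (Appendix 1).

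**5. Scale.** The exact interval for 5/30 is 5.6% to 34.7%, a width of 29 points. For 6/39, a pooled set, it is 5.9% to 30.5%, a width of 25 points.

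**The case for a change.** The strongest case for a change is that it would cost little: name the phase 2 patients as the main set, show the RP2D pool as supportive, and replace the optional FAS exclusion with a fixed baseline rule. Section 11.1 promises more detail in the SAP but does not promise to fix these two choices, and anti-tumor activity is a stated phase 2 objective. The calculation is not a strict upper bound either. Phase 2 results are shown by platinum stratum, and in an assumed stratum of 15 with 3 to 9 patients pooled, choosing the larger estimate adds 1.2 to 3.2 points over true rates of 10% to 45%.

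It stands that whether and when each option is used is unwritten, and that major and relevant are undefined. The rest weakens on inspection.

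- The text does contain rules on who qualifies. Pooling needs the same major criteria and the same dose regimen; exclusion needs a failed inclusion criterion, which is a pre-treatment fact. Neither refers to response.
- Sponsor approval of eligibility before dosing (section 6.2.7, carried to phase 2 by section 6.2.9.2) should keep FAS exclusions few.
- The dose-selection scenario is not the plan. Section 6.2.1.6 weighs PK, pharmacodynamics, safety and efficacy together, and the decision is shared with an external DMC. The supporting analyses in section 11.4.9 use disease control and tumor-size reduction, not ORR.
- Pooling need not flatter the result. If pooled phase 1 patients without a prior platinum response had an ORR of 5% (an assumption), choosing the larger estimate would add only 0.1 to 0.2 points at a phase 2 ORR of 15% to 20%. Routine pooling would lower the ORR by 1.7 to 3.5 points. If the prior-response criterion counts as major, which is the natural reading, those patients cannot be pooled at all.
- Phase 1 results are shown by dose level (section 11.1) and all imaging data are listed (section 11.4.7.1), so a reader could largely rebuild either set.

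**Conclusion.** No change is needed. The open point is whether and when two restricted options will be used, which a SAP ordinarily settles and analysts can fill sensibly. Choosing the larger estimate after the fact would raise the ORR by about 1 to 2 points (true ORR 10% to 20%, equal in both phases, 6 to 19 pooled), with interval coverage still above 95%. Adding two exclusions takes the shift to 2.3 points at 15% and, under the higher 30% assumption, 3.7 points. All of these are small beside an interval about 29 points wide, and they arise only if the choice follows the results.

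No test, threshold or power claim depends on the ORR, and the primary adverse event analysis uses the safety set, which includes every dosed patient (section 11.3.2). Making the phase 2 patients alone the main set would also widen the interval by about 4 points (29 against 25) in exchange for cleaner separation from phase 1. That is a fair trade-off on which statisticians differ, not the correction of an error.
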